4 INTRODUCTION

North American diets are heavy in carbohydrates which constitute approximately 55% of the macronutrients in an average person's diet. Overconsumption of refined carbohydrates may have harmful effects. For instance, high intake of sugar may lead to a 44% increased prevalence of metabolic syndrome and obesity and a 26% increase in developing diabetes mellitus (1).

A typical ketogenic diet consists of high-fats, moderate protein, and an extremely low amount of carbohydrates. Along with a major reduction in carbohydrates, dietary protein is decreased. People who choose a ketogenic diet instead use an alternative fuel source for the brain with the release of ketone substrates from the body (2). During periods of low blood sugar, the body begins to break down stored fat into ketone bodies (ketosis). The typical dietary ratio of fats to carbohydrates and proteins in a ketogenic diet ranges from 3:1 to 4:1 (3). With ketogenic diets substantial weight loss can be observed in as little as 2 weeks after initiation with strong preservation of lean body mass (1).

The therapeutic benefits that come with ketogenic diets are well documented. For example, low-carbohydrate ketogenic diets have been shown to significantly increase weight loss (4). Studies have shown that ketogenic diets can result in a reduction of mean body weight by 6.6% and serum triglyceride decrease by 42% (5). In comparison to low-fat diets those on ketogenic diets lose substantially more fat mass than fat-free mass, and have greater reductions in serum triglyceride levels (4). Adherence to a ketogenic diet may help to maintain a healthy weight and BMI over the long term (6). Also noted by Dashti was a significant reduction in blood glucose levels following a 24 week period of ketogenic diet treatment (6). A randomized, double-blind, placebo controlled trial has even demonstrated that ketogenic diets are excellent at preserving good nutritional status (7). More recently ketogenic diets have shown therapeutic benefits in maintaining skin health, decreasing serum triglyceride levels, and increasing high-density lipoprotein (4, 8). For example, in type 2 diabetes mellitus patients, ketogenic diets have been shown to improve glycemia control in the absence of type 2 diabetes' medication (5).

Low-density lipoprotein (LDL) is a combination of fat (lipid) and protein. The lipids are bound to the proteins, which allows them to move freely through the blood (9). LDL is often thought of as "bad" cholesterol being attributed to negative effects on cardiovascular health (10). Numerous studies, however, have indicated there is no association between LDL and negative cardiovascular health risks (11-13). In fact, a study conducted on 304 women determined there to be no association between LDL-C and coronary calcification in women over the age of 55 (14). The hypothesis that high levels of LDL reduce cardiovascular health may be founded on selective exclusion of data and misleading statistics (11). For example, a meta-analysis published in 2007, 61 studies examined the association between LDL and cardiovascular health risk. The results of the analysis, however, did not include twelve different studies that showed no association or an inverse association with LDL and decreased cardiovascular health. Part of the issue is there are often overlooked factors, such as mental stress that can raise cholesterol levels and cause hypertension or platelet aggregation (15).

There are various ketogenic diets that differ in their composition of protein, fat, and carbohydrate. The main ones include a classical ketogenic diet, a medium chain triglyceride diet (MCT), a low glycemic index diet, and a modified Atkins diet. These different compositions result in different benefits based on the ratio of macronutrients and range of foods that are consumed. For example, the classical ketogenic diet is comprised of consistent foods, which results in little variation in ketones. Whereas a diet that is higher in protein like MCT allows for a greater volume to mix different kinds of fats (16).

The present study will investigate the effects of Nic's Ketogenic diet, comprised of 70% fat, 5% carbohydrate, and 25% protein on middle-aged males and females with mid-range elevated LDL. With the increasing evidence that LDL lacks in causation of decreased cardiovascular health risk further studies are warranted to examine the true relation of LDL and cardiovascular health risk. For example, a ketogenic diet study examined changes in LDL (17). Results from this study indicated that a ketogenic diet causes a shift of small dense LDL to large buoyant LDL, which may reduce negative risks associated with cardiovascular health. In this study the efficacy of Nic's Ketogenic diet in increasing LDL without cardiovascular health risk will be examined. The main outcome of the study is to investigate whether in periods of higher LDL there will be positive impacts on cardiovascular health and inflammation.

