5 STUDY OBJECTIVES

The objective of this study is to investigate the efficacy of Nic's Ketogenic Diet on cardiovascular health and inflammation in healthy adults with mildly elevated LDL-C.

Primary outcomes:

The change in inflammation, as assessed by the change in erythrocyte sedimentation rate (ESR) and C-reactive protein (CRP) following Nic's Keto Diet for 140 days. The main outcome of the study is to investigate whether in periods of higher LDL there will be positive impacts on cardiovascular health and inflammation.

Secondary outcomes:

Changes to the following parameters from baseline to day 140 at monthly intervals following Nic's Keto Diet:

1. Weight
2. Blood pressure (BP)
3. Lipid panel

Changes to the following parameters from baseline to days 70 and 140 following Nic's Keto Diet:

1. Body composition (total body fat (%), android fat (%), gynoid fat (%), android/gynoid fat ratio, and muscle mass (%)) as assessed by DEXA Scan

[figure not shown]
Changes to the following parameters from baseline to day 140 following Nic's Keto Diet:

1. HbA1c
2. Fasting glucose
3. Free Tri-iodothyronine (T3)

Safety outcomes:

1. Incidence of pre-emergent and post-emergent adverse events
2. Electrocardiogram (ECG) after 70 and 140 days of following Nic's Keto Diet
3. Vital signs: heart rate (HR)
4. Anthropometrics: BMI calculation
5. Clinical chemistry: alanine aminotransferase (ALT), aspartate aminotransferase (AST), total bilirubin, creatinine, electrolytes (Na⁺, K⁺, Cl⁻, P), HbA1c, fasting glucose, and estimated glomerular filtration rate (eGFR))
6. Hematology: white blood cell (WBC) count with differential (neutrophils, lymphocytes, monocytes, eosinophils, basophils), red blood cell (RBC) count, hemoglobin, hematocrit, platelet count, RBC indices (mean corpuscular volume (MCV), mean corpuscular hemoglobin (MCH), mean corpuscular hemoglobin concentration (MCHC), red cell distribution width (RDW), and mean platelet volume (MPV))

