7.4 Early Withdrawal

Personal reasons

As stated in the Informed Consent Form, a participant may withdraw from the study for any reason at any time.

Removal by Qualified Investigator

Participant discontinuation should be considered at the discretion of the qualified investigator. The circumstances of any discontinuation must be documented in detail in the participant file and final report. If possible, the evaluations planned for the end of treatment will be carried out at the time when the participant is withdrawn from the study. A participant leaving the study prematurely will NOT be replaced by another. It is understood by all concerned that an excessive rate of withdrawals can render the study uninterpretable, thus unnecessary withdrawal of participants should be avoided.

Criteria for removal of participants from the study includes:

Clinical reasons

A participant may be withdrawn from the study if, in the opinion of the qualified investigator, it is not in the participant's best interest to continue. Any participant who experiences a serious adverse event (SAE) may be withdrawn from the trial at the discretion of the qualified investigator. A participant will also be withdrawn due to adverse events causing clinically significant illness or the need for prohibited medication(s) during the trial. Any female participant who becomes pregnant during the course of the trial will be withdrawn.

Protocol violation

Any participant found to have entered this study in violation of the protocol will be discontinued from the study at the discretion of the qualified investigator. This will include any participant found to have been inappropriately enrolled (did not meet eligibility criteria). Participant non-compliance includes failure to show up for study visits, failure to take the investigational product as directed, or refusal to undergo study visit procedures. Participants who are found to be taking prohibited medications or supplements without the knowledge of the qualified investigator will also be withdrawn. Any major protocol deviations (i.e. those that increase the risk to participants and/or compromise the integrity of the study or its results) will result in participant discontinuation.

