8.2 Directions

Participants will be instructed to follow Nic's keto diet plan for 140 days. Clinic staff will instruct participants to record results from their ketone and glucose monitor for the determination of compliance. Participants daily caloric need will be assessed for each participant as 90% of their energy requirements for weight maintenance based on their calculated base metabolic rate (BMR) and an activity factor. Participants will be advised not to exceed 20 g of carbohydrate per day (up to 5% caloric intake) and to consume the remaining 70% of calories from fat sources and 25% from protein sources. In addition to Nic's Keto Diet e-book, participants will be provided with a book summary and guidelines of foods that can be consumed and those that should not be consumed will be provided to the participant.

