11 STATISTICAL EVALUATION

11.1 Determination of Sample Size

Because this is a pilot study to explore the efficacy and safety of Nic's Ketogenic Diet, sample size will not be calculated. A total of 14 participants will be enrolled.

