11.3 Statistical Analysis Plan

All test of significance will be performed at 2-sided, alpha level = 0.05 unless otherwise specified.

All the primary and secondary endpoints will be analysed as continuous variables.

For each primary and secondary endpoint, descriptive statistics including number of subjects, arithmetic mean, standard deviation, median, minimum and maximum values will be presented for each study day and for the changes from baseline (Day 0) to each subsequent study day.

Changes in continuous endpoints from baseline will be calculated as:

$$\text{Change to } V_i = \text{Value at } V_i - \text{Value at } V_{\text{baseline}}$$

The continuous endpoints will be analysed with Mixed Model for Repeated Measures (MMRM). The model will include baseline value and visit as independent variables. P-values for the changes from baseline will be obtained from the model. No adjustment on p-values for multiple primary endpoints will be made.

Missing data for the primary and secondary endpoints will be imputed with last-observation-carried-forward (LOCF) method or multiple imputation as a sensitivity analysis for ITT Population. No imputation will be performed for PP and Safety Population.

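### Sections 4 and 5 ask about cardiovascular risk and benefit at higher LDL, which 14 participants, ESR and CRP, and a baseline-and-visit model cannot answer

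*Combined protocol and SAP*

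**What the plan says.** The closing paragraph of Section 4 says that the efficacy of the investigational "diet in increasing LDL without cardiovascular health risk will be examined". Its next sentence names the main outcome, and Section 5 repeats that sentence under the primary outcomes: "whether in periods of higher LDL there will be positive impacts on cardiovascular health and inflammation". The opening objective in Section 5 also names efficacy on cardiovascular health.

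The measures and methods are these:

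- **Primary (Section 5):** ESR and CRP. Sections 1.3 and 9.9 schedule both at Visits 2 and 8 only; between those visits the only laboratory blood test is the lipid panel.
- **Secondary (Section 5):** blood pressure and lipid panel, among others.
- **Safety (Section 5):** adverse events, ECG and heart rate, among others.
- **Model (Section 11.3):** "The model will include baseline value and visit as independent variables".
- **Size (Section 11.1):** "A total of 14 participants will be enrolled". As the study is a pilot, "sample size will not be calculated".
- **Withdrawal (Section 7.4):** "A participant leaving the study prematurely will NOT be replaced by another".
- **Safety analysis (Section 11.3.2):** adverse events as number and percentage of subjects; continuous safety parameters summarised descriptively. ECG is not among the parameters listed.

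**The concern.** Two different questions are posed. The Section 4 sentence is about no harm: LDL goes up and cardiovascular risk does not. The main-outcome sentence is about benefit while LDL is high. The first needs a measure of cardiovascular risk, a limit on how much harm would be acceptable, and enough information to exclude more than that. The second needs inflammation and LDL to be observed together over time and linked in the analysis. The plan provides neither set.

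This matters because participants are enrolled with LDL-C already in the 2.5–4.1 mmol/L range (Section 7.1) and a further rise is treated as something the diet should bring about. If few or no events occur and the markers do not change significantly, the stated aim invites a reassuring reading that the data could not carry.

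**Working it through.** **1. Sample size.** The plan gives 14 with no power, effect size, SD, event rate or margin, so there is no calculation to reproduce. What follows asks what 14 participants can show.

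**2. Zero-event limit.** Inputs: n = 14 (Section 11.1) and 140 days on the diet (Section 8.2). With 0 events in n people the exact upper limit is 1 − α^(1/n), with α = 0.05 for a one-sided 95% limit and α = 0.025 for the upper end of a two-sided 95% interval.

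| n evaluable | One-sided | Two-sided |
|---|---|---|
| 14 | 1 − 0.05^(1/14) = 19.3% | 1 − 0.025^(1/14) = 23.2% |
| 12 (assumed) | 22.1% | 26.5% |
| 10 (assumed) | 25.9% | 30.8% |

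The plan states no dropout rate, so 12 and 10 are illustrations only.

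**3. Chance of seeing any event.** Full exposure is 14 × 140/365.25 = 5.37 person-years. For an annual rate r, the 140-day risk is p = 1 − exp(−r × 140/365.25), and the chance of at least one event is 1 − (1 − p)^14. The documents give no event rate, so a range is assumed.

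| Assumed annual rate | Expected events | Chance of any event | Chance if the rate doubled |
|---|---|---|---|
| 0.2% | 0.011 | 1.1% | 2.1% |
| 0.5% | 0.027 | 2.6% | 5.2% |
| 1% | 0.054 | 5.2% | 10.2% |
| 2% | 0.107 | 10.2% | 19.3% |

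Zero events is the likely result whether or not the rate doubles, so it does not separate harm from no harm.

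**4. Continuous markers.** As an approximation, take a paired comparison at n = 14 and two-sided 0.05 (the level set in Section 11.3). The 95% confidence half-width is t(0.975, 13)/√14 = 2.160/3.742 = 0.58 SD of the change. A mean change of 0.81 SD is needed for 80% power. A non-significant change is therefore compatible with a shift of moderate size in either direction.

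**5. Periods of higher LDL.** LDL is measured at every visit from screening to day 140. ESR and CRP have one scheduled value before the diet and one at day 140. With a single scheduled post-baseline value, the visit term has one level for these two outcomes and the model reduces to change adjusted for baseline. It compares no periods, and no term relates LDL to ESR, CRP or anything else.

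**6. Attribution.** The model has no group term. Section 8.2 also sets intake at 90% of the energy needed for weight maintenance, so a marker change could reflect reduced intake or weight change rather than LDL. Section 6 carries no text in the copy reviewed; that there is no control group is inferred from the model and from the single diet described.

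**The case against.** The strongest reply is that this is a labelled pilot, that the no-risk phrase occurs only in the Introduction, and that an aim to be examined is not a claim. Nothing in Sections 11.1 to 11.3.2 treats a non-significant result or zero events as evidence of safety, and safety data are to be summarised descriptively. The plan also sets no hypothesis about events, so an event-risk limit tests something it did not promise.

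Much of this stands, and it rules out several readings a reader might be tempted by:

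- *That there is no cardiovascular endpoint.* Blood pressure and the lipid panel are secondary outcomes, and ECG and heart rate are safety outcomes. What is missing is a clinical-event or vascular endpoint and a non-harm margin.
- *That events will not be counted.* Section 11.3.2 counts adverse events by system organ class. Only an interval is lacking.
- *That Section 5 restates the no-risk claim.* It repeats the benefit sentence, which is a different question.
- *That a null result will be reported as absence of risk.* That would be a forecast; the documents contain no such rule.
- *That 10 is the expected safety denominator.* The Safety Population is everyone who starts the diet and has any safety information (Section 11.2), and Section 10.2.2 keeps participants who stop the diet in follow-up.

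The pilot label explains the small sample. It does not make the main-outcome question answerable, and that question stands under the primary outcomes, not only in the background.

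**Conclusion.** The concern holds in limited form: the stated aims go beyond what the measures, schedule and model can deliver. The study can describe short-term changes in ESR, CRP, lipids, blood pressure, heart rate and ECG, and list adverse events. It cannot support a conclusion that LDL rises without cardiovascular risk, nor that higher LDL goes with cardiovascular benefit.

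The 19.3% and 23.2% limits need only the planned 14 participants, all observed for 140 days without an event. The limits for 10 or 12, and the annual event rates, are assumptions. The figures in SD units use a paired t approximation to the planned model. A reader might go further and infer that the study can say nothing at all about cardiovascular matters; the secondary and safety measures do not support that reading.

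**What to change.** Revise the no-risk and main-outcome sentences in Section 4, and the opening objective and main-outcome sentence in Section 5. In place of the risk and benefit wording, describe changes from baseline over 140 days in ESR, CRP, the lipid panel including LDL-C, blood pressure, heart rate and ECG.

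Add a statement that no conclusion will be drawn on cardiovascular risk, on its absence, or on a relation between LDL and any outcome.

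In Section 11.3.2, report cardiovascular adverse events in the Safety Population with an exact upper confidence limit, stating whether it is one- or two-sided, and add a descriptive summary of ECG. Section 1.3 schedules an ECG at Visit 2, but the Visit 2 list in Section 9.2 omits it; these must be reconciled before a change from baseline in ECG can be described.

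This takes a few sentences, one interval and one ECG summary, with no new visits or samples beyond those in the Section 1.3 schedule. The downside is a less favourable headline claim.

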5 STUDY OBJECTIVES

The objective of this study is to investigate the efficacy of Nic's Ketogenic Diet on cardiovascular health and inflammation in healthy adults with mildly elevated LDL-C.

Primary outcomes:

The change in inflammation, as assessed by the change in erythrocyte sedimentation rate (ESR) and C-reactive protein (CRP) following Nic's Keto Diet for 140 days. The main outcome of the study is to investigate whether in periods of higher LDL there will be positive impacts on cardiovascular health and inflammation.

Secondary outcomes:

Changes to the following parameters from baseline to day 140 at monthly intervals following Nic's Keto Diet:

1. Weight
2. Blood pressure (BP)
3. Lipid panel

Changes to the following parameters from baseline to days 70 and 140 following Nic's Keto Diet:

1. Body composition (total body fat (%), android fat (%), gynoid fat (%), android/gynoid fat ratio, and muscle mass (%)) as assessed by DEXA Scan

[figure not shown]
Changes to the following parameters from baseline to day 140 following Nic's Keto Diet:

1. HbA1c
2. Fasting glucose
3. Free Tri-iodothyronine (T3)

Safety outcomes:

1. Incidence of pre-emergent and post-emergent adverse events
2. Electrocardiogram (ECG) after 70 and 140 days of following Nic's Keto Diet
3. Vital signs: heart rate (HR)
4. Anthropometrics: BMI calculation
5. Clinical chemistry: alanine aminotransferase (ALT), aspartate aminotransferase (AST), total bilirubin, creatinine, electrolytes (Na⁺, K⁺, Cl⁻, P), HbA1c, fasting glucose, and estimated glomerular filtration rate (eGFR))
6. Hematology: white blood cell (WBC) count with differential (neutrophils, lymphocytes, monocytes, eosinophils, basophils), red blood cell (RBC) count, hemoglobin, hematocrit, platelet count, RBC indices (mean corpuscular volume (MCV), mean corpuscular hemoglobin (MCH), mean corpuscular hemoglobin concentration (MCHC), red cell distribution width (RDW), and mean platelet volume (MPV))

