9.7.5 Dual Energy X-Ray Absorptiometry (DEXA) Scan

The DEXA scan will be performed at the KGK clinic (London, ON) or a local facility at visits 2 (Day 0), visit 5 (Day 84), and visit 7 (Day 140) by trained technicians. The DEXA scan is a form of X-ray radiation that measures the body tissue density which will be converted and used for assessment of the study outcomes. Coordinators will remind participants 24 hours before the day of the DEXA assessment for the necessary instructions prior to the scan.

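### The DEXA endpoints are all percentages or a ratio, so on an energy-restricted diet a participant who loses muscle can be scored as gaining it

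*Combined protocol and SAP*

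**What the plan says.** Section 5 makes body composition a secondary outcome and defines it as "Body composition (total body fat (%), android fat (%), gynoid fat (%), android/gynoid fat ratio, and muscle mass (%)) as assessed by DEXA Scan". The heading above that item reads "Changes to the following parameters from baseline to days 70 and 140". So there are four percentages and one ratio. No fat, lean or muscle mass in kilograms is named as an endpoint in Section 5, and the safety outcomes do not cover lean tissue either.

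Section 9.7.5 says only that the scan measures "body tissue density which will be converted and used for assessment of the study outcomes". Neither muscle mass (%) nor its denominator is defined.

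Section 11.3 states: "All the primary and secondary endpoints will be analysed as continuous variables". Change is the visit value minus the baseline value, and p-values for change come from a mixed model for repeated measures, two-sided at 0.05.

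Section 8.2 gives the energy target: "Participants daily caloric need will be assessed for each participant as 90% of their energy requirements for weight maintenance". Section 9.7.7 has participants told to expect water weight loss. Weight is a separate secondary outcome (Section 5) and is measured on calibrated scales at all visits (Section 9.7.1).

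**The concern.** A percentage of body weight changes when its denominator changes. Here the diet is set below maintenance energy, so the denominator is expected to fall during follow-up. The muscle percentage then mixes two things: what happened to muscle and what happened to everything else. A positive change need not mean that muscle was gained, or even kept.

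The Introduction makes this relevant. It says that with ketogenic diets "substantial weight loss can be observed in as little as 2 weeks after initiation with strong preservation of lean body mass", and that such dieters lose more fat mass than fat-free mass. Both statements are about amounts of tissue. Mostly-fat loss is also the pattern in which the muscle percentage goes up while the amount of muscle may go down. Participants are healthy adults with BMI from 20.0 to 29.9, so a rise in muscle percentage could be read as preservation or gain when the scans show a loss.

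The other endpoints share the limit. An android/gynoid ratio, for instance, does not move if both depots shrink by the same fraction.

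**Working it through.** The plan gives no sample-size calculation (Section 11.1) and no body-composition figure, so there is no planned number to reproduce. The check is algebra with a range of assumed inputs.

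**Inputs**
- Energy intake at 90% of maintenance: Section 8.2.
- Weight loss of 6.6%: the figure cited in the Introduction, used as an illustration. I also use 3% and 10%.
- Baseline weight of 80 kg: my assumption.
- Baseline muscle share of weight of 40%, 55% or 70%: my assumption. It is ranged because the documents give no figure and do not say whether muscle means muscle alone or all lean tissue.
- Denominator is total body weight: my assumption.

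**Formula.** Let W be baseline weight, m0 the baseline muscle share, dW the weight lost and s the share of the lost weight that is muscle.

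New share = (m0·W − s·dW) / (W − dW)

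Change in share = (m0 − s) · dW / (W − dW)

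The sign depends only on whether s is below or above m0. It does not depend on W or on the size of the weight loss.

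**Numbers at 6.6%.** dW = 0.066 × 80 = 5.28 kg and W − dW = 74.72 kg, so the multiplier is 5.28 / 74.72 = 0.07066. Example at m0 = 40%, s = 25%: (32 − 1.32) / 74.72 = 41.06%, a change of +1.06 points.

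| Muscle share of loss | Muscle change (kg) | m0 = 40% | m0 = 55% | m0 = 70% |
|---|---|---|---|---|
| 0% | 0 | +2.83 | +3.89 | +4.95 |
| 25% | −1.32 | +1.06 | +2.12 | +3.18 |
| 40% | −2.11 | 0.00 | +1.06 | +2.12 |
| 55% | −2.90 | −1.06 | 0.00 | +1.06 |
| 70% | −3.70 | −2.12 | −1.06 | 0.00 |
| 85% | −4.49 | −3.18 | −2.12 | −1.06 |

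(The last three columns are the change in muscle percentage, in points.)

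The break-even muscle loss is m0 × 5.28: 2.11, 2.90 and 3.70 kg. Any loss below that is scored as a gain. The first row shows that weight loss alone, with no change in muscle, moves the percentage up by 2.83 to 4.95 points.

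**Other weight losses, s = 25%.** At 3% the multiplier is 2.4 / 77.6 = 0.03093: muscle falls 0.60 kg and the percentage rises 0.46, 0.93 or 1.39 points. At 10% it is 8 / 72 = 0.1111: muscle falls 2.00 kg and the percentage rises 1.67, 3.33 or 5.00 points.

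**Fat percentage.** Treat the body as 24 kg fat and 56 kg lean. If 85% of the 5.28 kg lost is lean, fat falls by 0.15 × 5.28 = 0.79 kg, yet fat percentage rises 1.06 points, because (24 − 0.792) / 74.72 = 31.06%.

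**In kilograms.** Every row of the table below the first is scored as a loss, whatever m0 is.

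**The case against.** The best reply has four parts.

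First, a reader might infer that anyone who loses muscle while losing weight will be scored as gaining it. That does not follow. At a 40% baseline share, the percentage is unchanged when 40% of the loss is muscle, and falls when more of it is. How often the sign misleads depends on an unknown share and an undefined denominator. This stands, and it is why the point says *can*.

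Second, a reader might infer that the study cannot assess lean preservation, or that a harm would be hidden. The documents do not support that either. Weight is taken at every DEXA visit, so if the denominator is body weight, each participant's muscle in kilograms can be computed as percentage times weight. Lean preservation appears only as background in the Introduction. The stated objective is cardiovascular health and inflammation, with ESR and CRP as primary outcomes, and no section calls a higher muscle percentage favourable. What remains is that the derivation is not planned, depends on a denominator the protocol leaves open, and cannot be recovered exactly from separate group means of percentage and weight.

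Third, the 6.6% comes from a cited study whose title concerns type 2 diabetes, and diabetes is excluded here. This limits the kilogram figures as forecasts. It does not touch the sign.

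Fourth, kilograms are not free of ambiguity. Some early weight loss may be water (Section 9.7.7), and the documents do not say how the scan would count it. That calls for a caveat, not for percentages alone.

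Section 9.7.5 also says "The DEXA scan will be performed at the KGK clinic (London, ON) or a local facility". One might infer that a participant's scans will be on different machines. The text does not say so and gives nothing to size it with, so it is no part of this point.

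**Conclusion.** The point holds in conditional form. All five DEXA endpoints are relative measures, the plan expects weight to fall, and the muscle percentage can therefore rise while muscle falls. With 80 kg, a 6.6% weight loss and a quarter of the loss as muscle, a 1.32 kg loss appears as a gain of about 1 to 3 points across baseline shares of 40% to 70%. The effect vanishes when the muscle share of the loss equals the baseline share, and above that the percentage moves in the right direction.

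This rests on body weight being the denominator and on assumed baseline shares. The mostly-fat loss described in the Introduction makes the misleading case plausible, but the documents do not show how often it would occur. It concerns a secondary outcome in a 14-person pilot and leaves the primary analysis untouched. It merits a change because the remedy costs almost nothing.

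**What to change.** In Section 5, add change from baseline in total fat mass (kg) and lean mass (kg) from the DEXA scans already planned, analysed as in Section 11.3. Keep the percentages and the ratio. Define muscle mass (%): which scan quantity is the numerator and which mass is the denominator.

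State in Section 11.3 that any conclusion about muscle or lean preservation rests on the kilogram values read alongside the change in weight, with a note that early water loss may contribute.

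Reconcile the scan timing at the same time. Section 9.7.5 places the scans at Visit 5 (Day 84) and Visit 7 (Day 140). Section 5 gives Days 70 and 140, Section 9.4 puts Visit 5 at Day 70, and Section 9.6 makes Day 140 Visit 8. The new endpoints need one consistent set of visits and days.

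Cost: a few sentences, two more secondary endpoints, and extra data fields from existing scans. No visit, scan or participant is added. The muscle result may look less favourable than the percentage alone.
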